I, the undersigned, have reviewed this protocol, including the appendices and I will conduct the study as described in compliance with this protocol, GCP and relevant International Council on Harmonisation (ICH) guidelines.

Once the protocol has been approved by the Human Research Ethics Committee (HREC), I will not modify this protocol without obtaining prior agreement and approval from CSIRO/A*STAR Principal Investigator (PI) and the HREC. I will submit the protocol modification and/or any Informed Consent Form (ICF) modifications to the CSIRO/A*STAR PI and HREC and approval will be obtained before any modifications are implemented.

I understand that all the information obtained during the conduct of the study with regard to the participants' state of health will be regarded as confidential. No participants' names will be disclosed. All Participants will be identified by assigned numbers on all case report forms (CRF), laboratory samples or source documents. Clinical information may be reviewed by regulatory agencies. Agreement must be obtained from the participant before disclosure of participant information to a third party.

INVESTIGATOR SIGNATURE:

PRINTED NAME: [name]

COMPANY/POSITION: CSIRO

SIGNATURE: 

INVESTIGATOR SIGNATURE:

PRINTED NAME: [name]

COMPANY/POSITION: A*STAR

SIGNATURE: 

Study Synopsis

Protocol Title:	Bioavailability of omega-3 long-chain polyunsaturated fatty acids (LCPUFA) from foods enriched with vegetable-encapsulated omega-3 oils
Aim:	To compare the bioavailability of omega-3 LCPUFA from two test food products containing vegetable-encapsulated omega-3 algal oil against a control test product (algal oil gel capsules) across two ethnicities (Australian European vs. Chinese Singaporean).
Study Design:	Multi-centre, randomised, controlled, acute, 3-way cross-over study design. Participants will consume in random order, at least 1-week apart, three test products after an overnight fast. Blood samples will be collected at 0, 2, 4, 6, 8 and 24 hours after consuming the products. Plasma fatty acid concentrations ($\mu\text{g/mL}$) will be analysed by gas chromatography and bioavailability of omega-3 LCPUFA determined by calculating the incremental area under the curve ($i\text{AUC}_{0-24\text{h}}$), time to maximal value (T_{max}) and maximal value (C_{max}).
Study sites:	CSIRO Nutrition and Health Research Clinic, Adelaide A*STAR Clinical Nutrition Research Centre, Singapore

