
Some of the challenges in the production of foods fortified with omega-3 fatty acids include their undesirable odour and taste and their susceptibility to oxidative degradation (16). CSIRO has developed a novel vegetable-based encapsulation system for delivery of omega-3 LCPUFA which provides superior protection against oxidation of omega-3 fatty acids compared to other commercially available microencapsulation techniques (17), while at the same time delivering the nutritional benefits of vegetable consumption. Vegetable encapsulated omega-3 fortified food has the potential to deliver daily recommended dosage of omega-3 fatty acids (~250-500 mg/serve) in addition to a serving of vegetables. In addition, if a vegetarian omega-3 LCPUFA oil is used (e.g. algal oil), these products will also be suitable for vegans and vegetarians. One of the challenges in incorporating vegetable encapsulated omega-3 LCPUFA into fortified foods is the potential effect of the vegetable carrier matrix (e.g. fibre and other bioactives) on release and bioavailability of omega-3 LCPUFA *in vivo*. Furthermore, there is a possibility of inter-ethnic differences in omega-3 bioavailability. Heritability and anthropometric phenotypes, previously associated with omega-3 status (18), differ between Asian and Caucasian populations. The current project aims to address these challenges and to use the data generated as the basis for development of personalised formulations tailored to improve omega-3 status and vegetable intake and consequently health outcomes of consumers in Australia and Singapore.

2. Aim, Objectives and Hypotheses

Aim:

To evaluate the bioavailability of omega-3 LCPUFA from foods enriched with vegetable-encapsulated omega-3 oils across two ethnicities.

Objective/s:

- To compare the bioavailability of omega-3 LCPUFA from two test food products containing vegetable-encapsulated omega-3 algal oil against a control test product (algal oil gel capsules).
- To evaluate whether ethnic background (Australian European vs. Chinese Singaporean) affects the bioavailability of omega-3 LCPUFA when consuming vegetable-encapsulated omega-3 products relative to a control test product.

Hypotheses:

H0: Delivery of omega-3 LCPUFA with vegetables as carriers does not impact bioavailability.

H0: Bioavailability of omega-3 LCPUFA is not influenced by inter-ethnic differences.

Outcomes:

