heating at 90 °C; addition of 2 mL methanol; acidification with 200 µL of acetyl chloride and heating at 90°C for 1 hr while vortexing approximately every 10min after which the samples will be returned to room temperature. Methyl esters will be extracted into 1.5 mL hexane and 1.0 µl aliquot injected onto a gas chromatographic column (DB – FastFAME, 20m x 0.18 mm from Agilent Technologies), using a PerkinElmer Clarus 690 gas chromatograph / Clarus SQ 8 T Mass Spectrometer with a split 50:1 injector. Fatty acids will be identified by comparison with authentic Sepelco 37 component FAME mix (Sigma-Aldrich, Australia) and verified using the NIST MS search database software. Peaks will be measured using TurboMass software and fatty acids will be calculated against the internal standard.

8. Statistical analysis

A sample size of n=10 per site provides >80% power to detect a difference of 10% in AUC (22). N=12 per site will be recruited to account for a 20% attrition rate.

A statistical analysis plan will be developed before statistical analysis commences. In brief, data will be presented as means and SD/SEM. Plasma DHA and total omega-3 LCPUFA concentrations will be plotted into graphs. $iAUC_{0-24h}$ (primary outcome), will be calculated using the trapezoidal rule and corrected to baseline levels. Time to maximal value (Tmax) and the maximal value (Cmax) will be determined. Primary analysis will be pairwise comparisons between test foods vs. control using linear mixed models with fixed effects for treatment, time, ethnicity and assessing the interaction of treatment*time and treatment*time*ethnicity. Participant identifier will be fitted as a random effect, i.e. one intercept per participant. Potential covariates will be identified *a priori* and included in the model (e.g. BMI). Intention-to-treat analysis will be performed primarily and per protocol analysis as secondary analysis.

Statistical analysis will be performed using appropriate statistical packages e.g. SPSS software (IBM Corporation, New York, USA). Statistical significance will be determined at a *P*-value of <0.05. Statistical analysis will be performed blinded and treatments revealed after completion of the statistical analysis.

9. Assessment of Adverse Events

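### As listed in section 8, the treatment*time*ethnicity test lacks two lower-order ethnicity terms, so it mixes a common ethnic (or site) difference with the product-specific one that objective 2 asks about

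*Combined protocol and SAP*

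**What the plan says.** Section 8 (Statistical analysis) specifies linear mixed models with "fixed effects for treatment, time, ethnicity and assessing the interaction of treatment*time and treatment*time*ethnicity". The random part is a single intercept: "Participant identifier will be fitted as a random effect, i.e. one intercept per participant". Treatment*time is written out as its own term, so the asterisk does not read as shorthand that brings in every lower-order interaction. Time*ethnicity and treatment*ethnicity appear nowhere in the documents.

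The Study Synopsis fixes the factor levels. The trial is a "Multi-centre, randomised, controlled, acute, 3-way cross-over study design", and "Blood samples will be collected at 0, 2, 4, 6, 8 and 24 hours after consuming the products". There are two ethnic groups, each recruited at one site only.

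Section 2 gives two ethnicity targets that are not the same:

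- The second objective asks whether ethnic background "affects the bioavailability of omega-3 LCPUFA when consuming vegetable-encapsulated omega-3 products relative to a control test product". That is a product-specific question.
- The second null hypothesis is broader: "Bioavailability of omega-3 LCPUFA is not influenced by inter-ethnic differences".

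Section 8 presents its model as a short summary and says that an analysis plan will be written before the analysis starts. It does not say how a significant three-way term will be interpreted.

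**The concern.** The three-way term is the only listed interaction that contains ethnicity, so it is the natural place to look for an answer to objective 2. A test of that objective should respond only when the food-versus-capsule difference varies between the ethnic groups. If the lower-order ethnicity interactions are left out, their degrees of freedom do not vanish. Software that builds the three-way term from the cells of the design assigns them to that term. The test then also responds when one group has a larger or differently timed rise after every product, the capsule included.

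Such a common difference is not far-fetched. The protocol's introduction itself raises possible inter-ethnic differences in bioavailability. Ethnicity also coincides with site, so a site difference in the response to all products would enter the same term. What is at stake is a claim that the encapsulated foods work differently in the two populations when they behave exactly like the capsule in both.

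**Working it through.** The plan gives no degrees of freedom or error rate for this test, so there is no figure of its own to reproduce.

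**Inputs from the documents.** Treatment 3 levels (Study Synopsis), time 6 levels (0, 2, 4, 6, 8, 24 h), ethnicity 2 levels, 12 men per group, random intercept per participant, significance level 0.05 (section 8). Time is taken as a categorical factor.

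**Step 1: degrees of freedom (no further assumption).** The design has 3 × 6 × 2 = 36 cells.

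| Terms in the model besides the three-way | Rank | Left for treatment*time*ethnicity |
|---|---|---|
| As listed: 1 + 2 + 5 + 1 + 10 | 19 | 36 − 19 = 17 |
| Plus time*ethnicity (5) | 24 | 36 − 24 = 12 |
| Plus treatment*ethnicity (2) as well | 26 | 36 − 26 = 10 |

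The genuine three-way interaction has 2 × 5 × 1 = 10 df. The other 7 are time*ethnicity (5, common to all products) and treatment*ethnicity (2, itself product-specific). The 5 are the source of the misreading.

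**Step 2: what leaks into the test.** Suppose one group's curve differs from the other's by δ·s(t) after every product, with no product-specific effect. For n men per group and residual SD σ, the 17-df F test has noncentrality

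λ = (n/2) × 3 × Σ[s(t) − s̄]² × (δ/σ)².

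Only deviations of s(t) from its own mean count. If s(t) is constant, the sum is zero, so λ = 0 and the test keeps its 5% level.

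**Step 3: size, under assumed values.** The documents give no residual SD and no curve shape. Assume s = 0, 0.3, 0.7, 1, 0.9, 0.4 at the six times, with σ and δ as fractions of the peak rise. Then s̄ = 3.3/6 = 0.55 and Σ(s − s̄)² = 2.55 − 6 × 0.3025 = 0.735. With n = 12, λ = 6 × 3 × 0.735 × (δ/σ)² = 13.23 × (δ/σ)². The F test has 17 and (24 − 2) × 17 = 374 df.

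| δ (common to all products) | σ | λ | Rejection, 17-df test as listed |
|---|---|---|---|
| 0.1 | 0.3 | 1.47 | about 8% |
| 0.2 | 0.3 | 5.88 | about 24% |
| 0.3 | 0.3 | 13.23 | about 55% |
| 0.2 | 0.2 | 13.23 | about 56% |
| 0.2 | 0.5 | 2.12 | about 10% |
| 0.2 | 0.8 | 0.83 | about 7% |

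Simulation with 4,000 trials per setting gave 8%, 24% and 55% for the first three rows. Rows 3 and 4 have the same λ, so their difference is only simulation error. The hierarchical 10-df test stays at 5% throughout.

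A second simulation used a slightly different curve (0, 0.4, 0.9, 1, 0.8, 0.4) and a common peak difference of 1 residual SD. The listed test rejected in 45% of trials at 10 per group and 57% at 12. Adding time*ethnicity alone, or the full set of two-way terms, brought this back to about 5–6%.

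**Step 4: what does not change.** The listed terms including the three-way already have rank 36, the same as the full factorial. The two models give identical fitted cell means, and therefore identical contrasts built from those means.

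**The case against.** The strongest objection is that section 8 is a summary ahead of a fuller plan. Its wording about assessing interactions may name only those of interest, not every term to be fitted. That stands: a reader might infer that the trial will fit the truncated model and report a common difference as product-specific, but the documents state neither. The point is conditional on the model being fitted as listed. It remains worth making because this is the only model specification available.

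Three further stronger readings are tempting, and the documents do not support them:

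- *Any ethnic difference in the curves would trigger the term.* A group with a constantly higher DHA level would not, because the ethnicity main effect is in the model. Simulated parallel shifts of 0.3 and 1.0 of the peak rise left rejection at 5%.
- *A significant result would be a wrong conclusion.* The second null hypothesis in section 2 is not product-specific. A common ethnic difference in the response makes it false, and rejecting it would be right. The error arises only if the result is read as answering objective 2.
- *The primary analysis is compromised.* The primary comparisons are pairwise, each food against control, and step 4 shows that such contrasts are unchanged. The primary outcome, iAUC, has one value per man and product and no time factor, so this issue does not reach it.

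It is also fair that the rejection rates depend on an assumed SD and curve shape. At a 10% difference, the only effect size the plan names (for AUC), the excess is small: about 8% against 5%.

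**Conclusion.** The concern holds in conditional and limited form. If the model is fitted as listed, the omnibus treatment*time*ethnicity test has 17 df instead of 10 and is not a clean test of objective 2. Five of the extra degrees of freedom carry an ethnic or site difference in the post-dose rise shared by all products. The degrees-of-freedom count rests only on the factor levels in the protocol and on time being categorical.

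The size of the resulting error is uncertain. It could be negligible or larger than one in two, depending on the common difference and the residual SD, as the table shows. Those rates further assume balanced data, independent residuals after the participant intercept, and the stated curve shape. The harm is confined to the interpretation of this one omnibus test.

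**What to change.** In the SAP, specify the concentration model with treatment, time, ethnicity, all three two-way interactions (treatment*time, time*ethnicity, treatment*ethnicity) and treatment*time*ethnicity. State that objective 2 will be answered from the 10-df three-way term of that model, or from contrasts that compare each food-minus-capsule difference between the two ethnic groups. Report time*ethnicity separately as the common ethnic difference, noting that it cannot be separated from site.

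The cost is one line in the SAP, settled before analysis. Seven degrees of freedom move out of the three-way term into lines of their own. The rank of the fixed-effects model stays at 36, so no residual degrees of freedom are lost, and no change to data collection or sample size is needed.

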- Primary outcome: Incremental area under the plasma DHA and total omega-3 LCPUFA concentration ($\mu\text{g/mL}$) curves ($i\text{AUC}_{0-24\text{h}}$)
- Secondary outcomes: Time to maximal value (T_{max}) and maximal value (C_{max}) on the plasma DHA and total omega-3 LCPUFA concentration ($\mu\text{g/mL}$) curves.

3. Study Population

N=24 (N=12 in Australia; N=12 in Singapore) healthy men. Men are chosen as study population to ensure a homogenous population.

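### The analysis named in section 8 contains no treatment × ethnicity test on iAUC, which the second objective needs, and ethnicity cannot be separated from site

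*Combined protocol and SAP*

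**What the plan says.** Section 2 (Aim, Objectives and Hypotheses) sets two objectives. The second is about ethnicity and bioavailability "when consuming vegetable-encapsulated omega-3 products relative to a control test product". The second null hypothesis is broader: "Bioavailability of omega-3 LCPUFA is not influenced by inter-ethnic differences". The primary outcome in the same section is "Incremental area under the plasma DHA and total omega-3 LCPUFA concentration" curves, taken over 0 to 24 hours.

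Section 8 (Statistical analysis) says iAUC will be "calculated using the trapezoidal rule and corrected to baseline levels". It describes the primary analysis as food-versus-control comparisons from a linear mixed model with main effects of treatment, time and ethnicity, "assessing the interaction of treatment*time and treatment*time*ethnicity". On the random part it says: "Participant identifier will be fitted as a random effect, i.e. one intercept per participant". The description is introduced as brief, and "A statistical analysis plan will be developed before statistical analysis commences".

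The Study Synopsis and section 4.1 restrict the Australian site to Australian Europeans and the Singapore site to Chinese Singaporeans. No section comments on the resulting overlap of site and ethnicity.

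**The concern.** Objective 2 is a difference of differences: food minus capsule in one group, compared with food minus capsule in the other. Section 8 names no term that delivers this on the primary outcome. An analyst who follows the text would either fit treatment and ethnicity to iAUC and have no test of objective 2, or model concentrations and report the three-way test. That test can be significant because curve shapes differ while the iAUC contrast does not, and the reverse can also happen.

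Two further matters affect how a result would be read. A difference between groups in overall bioavailability, which is what the second null hypothesis describes, could come from the site. And a concentration model whose only random effect is a participant intercept treats the six samples of one visit as no more alike than samples from different visits. If that is untrue, its tests do not have their nominal level.

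**Working it through.** **The plan's own figure.** Section 8 states that "A sample size of n=10 per site provides >80% power to detect a difference of 10% in AUC". This cannot be reproduced, because no SD is given and the comparison it refers to is not stated. Only the 10 per site is used below.

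**1. Terms available on iAUC.** There are 3 products and 2 groups, so 6 group-by-product means. Treatment plus ethnicity uses 1 + 2 + 1 = 4 parameters. The missing 6 − 4 = 2 df are treatment × ethnicity, one for each food against the capsules. With no time factor, neither named interaction exists here.

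**2. The three-way term on concentrations.** There are six sampling times: 0, 2, 4, 6, 8 and 24 h. With all lower-order terms in the model, the three-way term has 2 × 5 × 1 = 10 df. Net iAUC by the trapezoidal rule is one weighted sum over time. The area weights are 1, 2, 2, 2, 9, 8 (total 24). Subtracting 24 × baseline gives −23, 2, 2, 2, 9, 8 (total 0). The objective-2 question is this single combination for each food (2 df), not a 10-df omnibus test. It could be extracted as a contrast, but section 8 specifies none. Extraction also works only if area below baseline is counted, which the baseline-correction wording leaves open.

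**3. Site and ethnicity.** Ethnicity and site are the same column: a design with an intercept and ethnicity has rank 2, and adding site leaves it at 2. Write a group's mean iAUC on a product as product mean + group effect + site effect. In food minus capsule within a person, a site effect that is the same for every product drops out. In the group main effect it stays. A site effect that differs by product would remain in both.

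**4. Visit-to-visit variation in a concentration model.** Assumptions: residual SD 1; a participant-by-visit shift with SD v, constant within a visit; 10 per site; full factorial means; participant intercept only; no true differences.

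- Observations: 20 × 18 = 360. Residual df: 360 − 36 means − 18 for participants = 306, of which 20 × 2 − 4 = 36 lie between visits.
- Expected residual mean square: [36(1 + 6v²) + 270]/306, which is 1.176 for v = 0.5 and 1.706 for v = 1.0.
- True over assumed variance for a time-averaged food-versus-capsule difference: (1 + 6v²)/mean square = 2.5/1.176 = 2.1 and 7/1.706 = 4.1.
- The critical value of about 1.97 acts as 1.97/√2.125 = 1.35 and 1.97/√4.10 = 0.97, giving rejection rates of about 18% and 33%.
- For the 10-df three-way test the ratio is 1/1.176 = 0.85 and 1/1.706 = 0.59, so it is conservative: about 2% and 0.1%.
- A comparison at one time point is far less affected: 1.25/1.176 = 1.06 and 2/1.706 = 1.17, or about 5.6% and 6.9%.

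Simulation of 10,000 trials per setting agrees. The 2-df treatment × ethnicity test on net iAUC rejected 4.9% and 5.1%. A constant visit shift cancels in the zero-sum weights, and with one value per visit any other visit variation is part of the residual.

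**The case against.** The strongest reply is that section 8 is a summary and a fuller plan is promised, so the right test may yet be named. That stands to this extent: the point is what the SAP must specify, not proof that the final analysis will be wrong.

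It is also fair that bioavailability is judged by Tmax and Cmax as well as iAUC. With lower-order terms included, a three-way result says that product profiles differ by group. That bears on objective 2, but it does not answer it on the primary outcome.

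The overlap of site and ethnicity is built into the design, and no analysis removes it. That is why only the wording of conclusions can change.

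Four stronger readings are tempting, and the documents do not support them:

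- *A time-course difference common to all products would be reported as a treatment interaction.* This needs the list in section 8 to be the complete model, where the three-way term has 36 − 19 = 17 df instead of 36 − 26 = 10. For a list introduced as brief, that reading is unlikely.
- *The interaction is underpowered.* With no SD and no stated comparison, power for this contrast cannot be calculated.
- *The pooled food-versus-capsule comparisons are invalid.* They are mis-sized only if made on concentrations and only if visits vary. Made on iAUC, they are not affected.
- *Site differences invalidate objective 2.* Site effects equal for all products cancel, and the documents identify no product-specific one.

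**Conclusion.** The concern holds. As written, the plan names no test of its second objective on its primary outcome, and the three-way term it does name is not a substitute. This follows from the structure of the outcome and needs no numerical assumption. The identity of site and ethnicity is equally certain. It limits the second null hypothesis more than objective 2, because the two ask different questions.

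The mis-sizing is conditional. The rates of about 18% or 33% for time-averaged pairwise tests, and about 2% or 0.1% for the three-way test, rest on assumed visit SDs of 0.5 and 1.0 residual SD with 10 per site. With no visit variation, both kinds of test are near 5%. The documents give no figure for this variation. The matter should be fixed in the SAP before analysis.

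**What to change.** In the SAP, before analysis begins:

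(a) For iAUC over 0–24 h of DHA and of total omega-3 LCPUFA, fit treatment, period, ethnicity/site and treatment × ethnicity with a participant random intercept, plus any covariates the SAP adopts. Make the food-versus-capsule comparisons from this model, and name the 2-df treatment × ethnicity test as the test of objective 2. Period belongs in a three-period crossover, because dropout can unbalance the orders. With 10 per site it uses 2 of 60 − 6 − 18 = 36 residual df.

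(b) Report the between-group difference in soup-minus-capsule and in snack-minus-capsule iAUC, each with a 95% CI.

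(c) Treat any concentration-time model as supportive. Include all lower-order interactions, and add a participant-by-visit random effect to the participant intercept. Adding treatment × ethnicity without that random effect would carry the same mis-sizing into the ethnicity test.

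(d) Describe any group difference as a site/ethnicity difference, draw no ethnic conclusion from the main effect, and do not read a non-significant interaction as no difference.

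The cost is SAP text, with no new data or participants. The downsides are a more modest ethnicity claim and an interaction estimate that may be imprecise. Rewording the second hypothesis is optional; it would be a protocol change needing principal investigator and ethics committee approval.

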***Self-reported, no clinical testing will be performed.**

4. Study Design and procedures

A multi-centre, randomised, controlled, acute, 3-way cross-over single-blind study design will be used. The trial will be performed at CSIRO's Nutrition and Health Research Clinic, Adelaide (n=12) and A*STAR's Clinical Nutrition Research Centre in Singapore (n=12).

Participants will attend a screening visit to confirm their eligibility for inclusion into the trial (Figure 1). If eligible, participants will remain at the clinic where they will be enrolled into the study and participate in the first intervention on that day (Screening will be conducted at V1). After enrolment participants will attend the research clinic for test procedures on 3 occasions at least 1-week apart during which they will consume one of three test products at each occasion in random order. Participants will attend the clinic on 6 occasions in total (to include returning for 24hr blood sample) – visits 2, 4 and 6 (Figure 1). A 1-week washout period is sufficient for plasma sample to return to baseline (19). Participants will be randomly assigned by computer sequence generation (<http://www.randomisation.com>) to one of three treatment orders (Figure 1). The random allocation sequence will be generated by a staff member not involved with entering participants into the trial to ensure allocation concealment.

[figure not shown]

Figure 1. Study design

Participants will visit the research clinic on six occasions (Figure 1).

- Occasion 1: Screening + 1st intervention (randomised) involving in-clinic assessments (~9 hours).
- Occasion 2: Participants will return to the clinic for a short visit (30 minutes) where a 24-hour blood sample will be collected (Figure 2).
- Occasion 3: (1 week following Occasion 1) 2nd intervention (randomised) involving in-clinic assessments (~8.5 hours).
- Occasion 4: Participants return to the clinic for a short visit (30 minutes) where a 24-hour blood sample will be collected.
- Occasion 5: (1 week following Occasion 3) 3rd intervention (randomised) involving in-clinic assessments (~8.5 hours).
- Occasion 6: Participants return to the clinic for a short visit (30 minutes) where a 24-hour blood sample will be collected.

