Screening occasion: Participants will be pre-screened using a screening questionnaire and those determined to be potentially eligible will be invited to attend an in-clinic screening visit. After they have given signed informed consent (see details below) their eligibility will be confirmed by reviewing their medical history, demographic information and fatty fish intake obtained from the screening questionnaire, measuring height and weight and calculating BMI, and measuring vital signs (blood pressure and temperature). Eligible participants will be enrolled into the study and remain at the clinic for further 8.5 hours and complete their first intervention

Intervention occasions (Figure 2): Participants will arrive at the research clinic after an overnight fast (>10h)). Weight, percentage body fat mass and vital signs (blood pressure and temperature) will be measured, an intravenous cannula will be inserted into the participants arm for a duration of 8 hours during which the participant will remain at the research clinic.

A fasting blood sample (4 mL) will be collected after which participants will consume a standardised breakfast with their test product (see section 5 for more detail) within 15 minutes. Subsequent blood samples will be collected after 2, 4, 6 and 8 hours. The cannula will be removed, and participants will leave the research clinic. Participants will return to the research clinic the next morning after an overnight fast for collection of the 24-hour sample. The period of 24 hours was chosen as it represents an intake interval of daily intake of omega-3 supplements (19). Throughout the 9-hour day at the clinic participants will have access to low-fat snacks and a lunch meal devoid of omega-3 LCPUFA that they can consume *ad libitum* (see section 5 for more detail). Participants will leave the clinic with a take-home low-fat dinner meal.

Apart from the study specific test products, participants will be requested to maintain their habitual lifestyle patterns throughout the duration of the study and to avoid fatty fish and omega-3 LCPUFA containing supplements. Participants will be provided with a checklist to record any non-compliance or accidental consumption of these foods and return the checklist at their subsequent visit.

Staff responsible for sample and statistical analysis will be blinded to which treatment was consumed when, but participants and staff administering treatments will not be blinded.

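### If the mixed model is fitted to the repeated concentrations, its single participant intercept leaves visit-to-visit variation out of the time-averaged food-versus-control comparison; on iAUC0-24h the problem does not arise

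*Combined protocol and SAP*

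**What the plan says.** The model is described in section 8 (Statistical analysis) of the protocol. The main comparison is given as "Primary analysis will be pairwise comparisons between test foods vs. control". It comes from a mixed model whose systematic part is listed as "fixed effects for treatment, time, ethnicity and assessing the interaction of treatment*time and treatment*time*ethnicity". The random part is one sentence: "Participant identifier will be fitted as a random effect, i.e. one intercept per participant". Section 8 mentions no visit or period term, no participant-by-visit effect and no residual covariance over the sampling times.

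The design has two levels below the participant. Section 4 (Study Design and procedures) has each man attend on "3 occasions at least 1-week apart during which they will consume one of three test products at each occasion in random order". The synopsis sets the sampling within each visit: "Blood samples will be collected at 0, 2, 4, 6, 8 and 24 hours after consuming the products". That is 3 visits with 6 samples each, or 18 concentrations per man.

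The primary outcome, in the synopsis, section 2 and section 8, is iAUC0-24h, which "will be calculated using the trapezoidal rule and corrected to baseline levels". It gives one value per man per visit. Section 8 does not say which of the two, iAUC or concentration, is the model's response. It calls its description a summary and defers detail to a SAP to be written before analysis starts.

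**The concern.** Time and treatment-by-time have their usual sampling-time meaning only if the response is the series of concentrations, because an iAUC has no sampling-time dimension. A reader who implements section 8 literally would therefore fit the 18 concentrations per man with one intercept per man.

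That intercept makes all 18 values equally correlated. Samples from one visit also share that day's fasting level, meal and absorption, and the model has no term for this. Since the product is assigned to the visit, the visit is the experimental unit for food versus control, and the error of that comparison must contain visit-to-visit variation. If it does not, a pairwise treatment comparison averaged over the sampling times gets a standard error that is too small. The trial could then report that encapsulation changes DHA bioavailability, its main question, more often by chance than the stated 5%.

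**Working it through.** **The plan's own figure.** Section 8 gives no standard error or variance for this model. Its power statement (n=10 per site, 10% difference in AUC, over 80% power) comes without an SD, so it can be neither reproduced nor used to size this point.

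**Inputs.** From the documents: n = 24 men recruited (20 evaluable after attrition), k = 3 visits, m = 6 samples per visit, alpha 0.05 (taken as two-sided). Assumed: ρ, the visit-level share of within-person variance, from 0 to 0.5. The documents give no value for it.

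**Model for the check.** Concentration = participant + visit (variance ρ) + sample error (variance 1−ρ), with no true product difference. Ethnicity and covariates are left out for simplicity. The fit uses treatment, time, treatment-by-time and a participant intercept only.

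**Formulas.**
- Residual df of the fitted model: nkm − n − (km − 1) = 432 − 24 − 17 = 391. Of these, (n−1)(k−1) = 46 are between visits and 345 within visits.
- Residual variance that the model pools: s² = [46(1−ρ+6ρ) + 345(1−ρ)] / 391.
- Claimed variance of a visit mean: s²/6. True variance: ρ + (1−ρ)/6.
- SE ratio (claimed/true) = √[(s²/6) / (ρ + (1−ρ)/6)].

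**Worked case, ρ = 0.3.** s² = (46 × 2.5 + 345 × 0.7)/391 = 356.5/391 = 0.912. Claimed 0.912/6 = 0.152; true 0.3 + 0.7/6 = 0.417. SE ratio = √(0.152/0.417) = 0.60.

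**Time-averaged food-versus-control contrast, nominal 5%:**

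| Assumed ρ | SE ratio | False positives, approximation (n=24) | Simulated, n=24 (two sets) | Simulated, n=20 |
|---|---|---|---|---|
| 0 | 1.00 | 5.5% | 4.6%, 4.7% | 4.9% |
| 0.1 | 0.80 | 12.1% | 11.6%, 11.5% | 11.4% |
| 0.2 | 0.69 | 18.4% | 18.1%, 18.6% | 17.8% |
| 0.3 | 0.60 | 24.1% | 23.5%, 22.4% | 24.2% |
| 0.5 | 0.49 | 33.7% | 33.6%, 33.9% | 32.9% |

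With visit-level error the simulated rate stays near 5% throughout (4.3% to 5.3%). In 25 REML fits at n=20 and ρ=0.3, the mean SE was 0.123 without a participant-by-treatment (equivalently, by-visit) component and 0.200 with it, a ratio of 0.62.

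**Other contrasts under the same model (ρ from 0.1 to 0.5).**
- Single time point: SE ratio √s² = 0.99 to 0.92; false positives about 5.5% to 7%.
- Treatment-by-time: SE ratio √[s²/(1−ρ)] = 1.04 to 1.31, so the SE is too large. The overall test rejects 3.4%, 1.6%, 1.0% and 0.1% at ρ = 0.1, 0.2, 0.3 and 0.5.

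**Serial correlation instead of a shared visit effect.** With correlation decaying over the actual sampling hours, at 0.3, 0.5 and 0.7 over two hours, the time-averaged contrast rejects 11.7%, 18.3% and 27.2%, and treatment-by-time 3.5%, 2.8% and 1.7%. The directions are the same.

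**iAUC0-24h as response.** With one value per visit, a visit effect cannot be separated from the residual, so the residual already carries it. Simulated false positives (n=20) are 4.4% to 5.0% at every ρ.

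**The case against.** The strongest reply is that the named primary outcome is untouched: iAUC0-24h under a participant intercept keeps its 5%. This stands. A reader might infer that the trial's primary test is invalid, but the documents do not support that, because section 8 never says that concentration is the response. What remains is that section 8 attaches sampling-time terms to the model that delivers the primary comparisons, and those terms do not fit iAUC.

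Three other strong readings also go too far.
- That same-visit samples are treated as independent. The participant intercept does correlate them, only no more than samples from different visits.
- That every food-versus-control standard error is too small. This holds mainly for the time average, which the plan does not name as its estimand. It is slight at a single time point and reverses for treatment-by-time.
- That an error near 30% follows with no assumed visit share, because subtracting one fasting value from five post-dose samples alone creates a correlation of 0.5. The arithmetic is sound, but section 8 applies baseline correction to the iAUC and does not say that concentrations are corrected before modelling.

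It is also fair that ρ is assumed, that at ρ = 0 nothing is wrong, and that running each man's samples in one assay batch (section 7) removes one source of visit-level variance. Day-to-day fasting differences remain. Finally, the SAP is still to come and no residual covariance is ruled out. But the random part is spelled out as one intercept per participant, and a SAP that copies the sentence would copy the gap.

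**Conclusion.** The point holds conditionally. If the section 8 model is fitted to the repeated concentrations, the time-averaged food-versus-control contrast is tested against an error without visit-to-visit variation. Its standard error is then about 0.80 to 0.49 of the true value, and its false-positive rate about 11% to 33%, for assumed visit-level shares of 0.1 to 0.5. The size rests wholly on that assumed share. Treatment-by-time tests err the other way and lose power. For iAUC0-24h there is no defect. The underlying weakness is that the response variable is not stated. Severity: should-fix, conditional on concentrations being modelled.

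**What to change.** In the SAP:

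1. State that the primary food-versus-control test is on iAUC0-24h, with a participant random intercept and no sampling-time term.
2. For every concentration-by-time model, add a participant-by-visit random intercept. Alternatively, keep the participant intercept and add a within-visit residual covariance suited to the unequal spacing: unstructured, or spatial-power in actual hours. AR(1) by sample order is unsuitable, because it would treat the 16-hour gap from 8 to 24 h like the 2-hour gaps before it.
3. Use Kenward-Roger or Satterthwaite degrees of freedom in those models.

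The cost is a few lines of SAP text and about one line of code, with no change to data collection. The downside is wider confidence intervals for time-averaged product contrasts, which is the uncertainty that the design actually carries.
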